6.3. Preparation of Study Intervention

Before use, the vials are reconstituted with water for injection (8 mL) to obtain a solution containing 0.5 mg/mL lurbinectedin. For administration to participants as IV infusion, the reconstituted vials are diluted with glucose 50 mg/mL (5%) solution for infusion or sodium chloride 9 mg/mL (0.9%) solution for infusion.

In order to obtain reliable information during the first dosing, the infusion rate should not be modified once the infusion begins, especially during the first cycle. Lurbinectedin is administered as a 1-hour IV infusion.

6.4. Measures to Minimize Bias

Specific measures to minimize bias are not applicable to this open-label, nonrandomized study. All participants who sign the ICF will receive a participant number. The participant number identifies the participant for all study procedures that occur throughout the study. This number is unique and once assigned, cannot be reassigned to another study participant.

6.5. Study Intervention/Treatment Compliance

Participants who are dosed at the site will receive study intervention directly from the investigator or designee, under medical supervision. The date and time of each dose administered in the clinic will be recorded in the source documents and recorded in the eCRF. The dose of study intervention and study participant identification should be confirmed at the time of dosing by a member of the study site staff other than the person administering the study intervention.

6.6. Prophylactic Medication

All participants will receive mandatory prophylactic medications as indicated below. The IV formulation of these agents must be used in this setting:

- Corticosteroids (dexamethasone 8 mg or equivalent)
- Serotonin (5-HT₃) antagonists (ondansetron 8 mg or equivalent)
- Extended treatment with oral 5-HT₃ antagonists and oral dexamethasone for 2 consecutive days
- If necessary, and in addition to the above, administration of 10 mg of oral or IV metoclopramide (or equivalent) every 8 hours.
- Administration of primary prophylaxis of colony-stimulating factors such as G-CSF or GM-CSF is mandated starting from Cycle 1 and during all subsequent cycles. The type, dose, and scheme to be used may vary according to institutional/standard practices or guidelines. A mandatory window of at least 24 hours and up to 72 hours must be allowed from the last dose of study intervention administration until G-CSF or GM-CSF prophylaxis is started.

6.7. Study Intervention Dose Delay and Reduction Rules

For any treatment delay due to treatment-related AEs lasting more than 1 week, a dose reduction should be implemented upon recovery.

Participants may continue the study treatment at a reduced dose if they present any of the following:

- Grade ≥ 3 treatment-related nonhematological toxicity. Exceptions are Grade ≥ 3 nausea and/or vomiting not optimally treated, Grade 3 asthenia lasting ≤ 3 days, Grade 3 diarrhea lasting ≤ 2 days or not optimally treated, Grade 3 transient ALT/AST elevations that are rapidly reversible and not leading to subsequent delays, and nonclinically relevant biochemical abnormalities
- Grade 4 thrombocytopenia or Grade 3 thrombocytopenia concomitantly with Grade ≥ 3 bleeding
- Grade 4 neutropenia, any grade febrile neutropenia or neutropenia associated with infection/sepsis
 - Note: All participants receive mandatory colony-stimulating factors such as G-CSF or GM-CSF starting from Cycle 1 and during all subsequent cycles.

However, if the episode of neutropenia persists despite supportive care with G-CSF or GM-CSF, then the dose must be reduced

- Frequent or prolonged (> 1 week) dose delays due to treatment-related AEs
- Unacceptable toxicity in the judgement of the investigator

Participants who experience Grade ≥ 3 hypersensitivity reactions or Grade ≥ 3 rhabdomyolysis will be discontinued from study intervention.

Dose reduction levels are shown in Table 6.

Table 6: Lurbinectedin Dose Reduction Levels

Dose Reduction	Lurbinectedin Dose (mg/m ²)
1 (starting dose)	3.2
-1	2.6
-2	2.0

Up to 2 dose reductions are allowed per participant. Participants who continue to experience treatment-related toxicity and/or frequent dose delays after permitted dose reductions should be discontinued from the study. However, they can continue receiving the study intervention if objective clinical benefit is adequately documented by the Investigator, and upon agreement with the Sponsor. Once the dose has been reduced for an individual participant, it will not be re-escalated under any circumstance.

Participants not meeting criteria for continuation after a maximum of 3-week delay should be discontinued from the study. For delays > 3 weeks, retreatment can be considered on case-by-case basis after discussion with the medical monitor.

Details related to required follow-up laboratory tests to be performed after reporting of specific AEs are presented in [Section 8.3.4](#).

6.8. Continued Access to Study Intervention After the End of the Study

Not applicable.

6.9. Treatment of Overdose, Medication Errors, or Misuse

Overdose (defined as any dose administered or received that was higher than the intended dose), medication errors (defined as any unintentional error in the dispensing or administration of the study drug), and misuse of the study drug are considered reportable experiences.

There is currently no specific treatment in the event of an overdose with lurbinectedin, and possible symptoms of overdose have not been established. Lurbinectedin must only be used in accordance with the dosing recommendations in this protocol. Any dose or frequency of dosing that exceeds the dosing regimen specified in this protocol should be reported as an overdose.

In the event of an overdose, the investigator should:

- Contact the Medical Monitor immediately.
- Evaluate the participant to determine, in consultation with the Medical Monitor, whether study intervention should be interrupted or whether the dose should be reduced.
- Closely monitor the participant for any AE/SAE and laboratory abnormalities for at least 14 days.
- Document the quantity of the excess dose as well as the duration of the overdose.

6.10. Concomitant Therapy

Any medication or vaccine, including over-the-counter or prescription medicines, recreational drugs, vitamins, and/or herbal supplements that the participant is receiving at the time of enrollment or receives during the study must be recorded along with:

- Reason for use
- Dates of administration including start and end dates
- Dosage information including dose, frequency, and route

The Medical Monitor should be contacted if there are any questions regarding concomitant or prior therapy.

6.10.1. Allowed Concomitant Medications

The following medications are allowed during study participation:

- Colony-stimulating factors such as G-CSF or GM-CSF
 - Primary G-CSF or GM-CSF is mandated during the first and all subsequent cycles. The type, dose, and scheme to be used may vary according to institutional/standard practices or guidelines. A mandatory window of at least 24 hours and up to 72 hours must be allowed from the last dose of study intervention administration until G-CSF or GM-CSF prophylaxis is started.
- Therapies for pre-existing and treatment-emergent medical conditions, including pain management
- Blood products and transfusions, as clinically indicated
- Bisphosphonates
- Primary and secondary prophylaxis and/or symptomatic treatment for emesis according to ASCO guidelines for nausea or vomiting (see [Section 6.6; Hesketh, 2017](#))
- Erythropoietin treatment according to ASCO guidelines
- Anticoagulation therapy.

In addition to the above, all treatments that the Investigator considers necessary for a participant's welfare may be administered at the discretion of the Investigator in keeping with the

community standards of medical care. All concomitant medication will be recorded in the case eCRF including all prescription, OTC, herbal supplements, and IV medications and fluids. If changes occur during the trial period, documentation of the medication as per [Section 6.10](#) may also be included in the eCRF.

6.10.2. Prohibited Concomitant Medications

The following medications are prohibited during study participation:

- Any other antineoplastic therapy
- Any other investigational agents
- Immunosuppressive therapies other than corticosteroids for antiemetic prophylaxis and/or pain control
- Aprepitant, fosaprepitant or related compounds (other NK-1 antagonists)
- Radiotherapy

6.10.3. Lurbinectedin Drug-Drug Interactions

In vitro studies with human liver microsomes have shown that CYP3A4 is a major metabolic enzyme involved in lurbinectedin metabolism, followed by CYP2E1, CYP2D6, and CYP2C9. The contribution of other CYP isoenzymes is negligible. Thus, concomitant drugs which induce or inhibit CYP3A4 should be carefully monitored or avoided, whenever possible ([Appendix 7](#)). A significant interaction with aprepitant (CYP3A4 inhibitor) is suggested by available lurbinectedin phase 2 data from ovarian cancer patients and a phase 1 Study PM1183-A-008-13 in patients with advanced solid tumors, where lurbinectedin clearance was reduced by 42%, approximately, in the presence of aprepitant and resulted in unusually long-lasting neutropenia, as well as thrombocytopenia with a worse outcome. Although all patients eventually recovered, the use of aprepitant is not permitted.

Based on in vitro study results, lurbinectedin was shown to inhibit CYP2C8, CYP3A4, and CYP2B6. However, according to guidelines from European Medicines Agency and FDA (US), the calculated in vivo impact of lurbinectedin on those CYP isoenzymes was insignificant. Therefore, no potential drug-drug interaction is expected between lurbinectedin and drugs which are metabolized by CYP3A4, CYP2C8, or CYP2B6.

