5.5. Criteria for Treatment Continuation

Further treatment cycles (ie, Cycle 2 and after) will be administered Q3W if the participant fulfills all the retreatment criteria within 3 days prior to the scheduled lurbinectedin infusion (Table 3) and defined in Table 4.

Table 4: Criteria for Treatment Continuation (Cycle 2 and After)

Variable	Retreatment Criteria (Day 1)
Hemoglobin ^a	≥ 9 g/dL
ANC	≥ 1.5 × 10 ⁹ /L
Platelets	≥ 100 × 10 ⁹ /L
AST/ALT	≤ 3 × ULN; for participants with documented metastatic liver disease, AST and ALT levels ≤ 5 × ULN
Total serum bilirubin	≤ 1.5 × ULN
Serum creatinine	≤ 1.5 × ULN or creatinine clearance ≥ 30 mL/min
Events of rhabdomyolysis	Withhold for Grade 2; resume at same dose if Grade ≤ 1
Other nonhematological treatment-related AEs (except isolated increased GGT and/or AP; Grade 2 asthenia, constipation, alopecia, peripheral neuropathy, or nonoptimally treated nausea and/or vomiting)	Grade ≤ 1
Active infection (including sepsis) and/or bleeding (any grade)	Absence

Abbreviations: AE = adverse event; ALT = alanine aminotransferase; ANC = absolute neutrophil count; AP = alkaline phosphatase; AST = aspartate aminotransferase; GGT = gamma-glutamyltransferase; ULN = upper limit of normal.

^a Participants may receive packed red blood cells transfusion and/or erythropoietin treatment, if clinically indicated, to increase or maintain adequate hemoglobin levels.

If a participant does not meet the requirements for treatment continuation on Cycle 2 Day 1 or subsequent cycles, reassessments will be performed at least every 48 to 72 hours for evaluation of treatment continuation. Treatment can be withheld up to a maximum of 3 weeks. Lurbinectedin dose delay and reduction rules are presented in Section 6.7.

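### Strong CYP3A4 inhibitors and strong non-antineoplastic inducers are not prohibited, and the monitoring they call for is neither specified nor graded by potency

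*Protocol*

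**What the plan says.** Protocol 6.10.3 identifies CYP3A4 as a major enzyme in lurbinectedin metabolism. It reports that "lurbinectedin clearance was reduced by 42%, approximately, in the presence of aprepitant", with prolonged neutropenia and thrombocytopenia, and does not permit aprepitant. Protocol 6.10.2 lists aprepitant as prohibited, together with fosaprepitant and other NK-1 antagonists. It also prohibits other antineoplastic therapy.

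For CYP3A4-active drugs in general, 6.10.3 says that "concomitant drugs which induce or inhibit CYP3A4 should be carefully monitored or avoided, whenever possible", and points to Appendix 7. Table 12 in that appendix ranks agents by potency but describes itself as examples and attaches no action to any rank.

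Protocol 6.10.1 lists as allowed "Therapies for pre-existing and treatment-emergent medical conditions, including pain management", and adds that other treatments the investigator considers necessary "may be administered at the discretion of the Investigator". That discretion is not made subject to 6.10.2. Protocol 6.10 adds: "The Medical Monitor should be contacted if there are any questions regarding concomitant or prior therapy".

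**The concern.** The sponsor did not leave aprepitant to site judgement. For agents that Table 12 ranks above aprepitant, it does. Two sites could read the same sentence differently: one might avoid voriconazole altogether, while another gives it and regards the routine counts as careful monitoring.

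The stake is participant safety, in both directions. An inhibitor raises lurbinectedin exposure. An inducer lowers it, and the participant may then receive less effective treatment with nothing in the counts to show it. Protocol 4.3 reports reduced efficacy at lower doses and more severe haematological toxicity at higher ones. That analysis is in SCLC, so only its direction carries over.

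There is also a reporting consequence. Concomitant medications are recorded and summarised (Protocol 6.10.1, SAP 8.9). Because these agents are not prohibited, their use would not count under the prohibited-medication subtype of important deviations in SAP 8.3.

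**Working it through.** No sample size, error rate or analysis figure depends on this point. The check compares sections and adds simple arithmetic for scale.

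**1. Which agents fall outside the prohibition (6.10.2 against Table 12)**
- Prohibited: aprepitant (moderate) and fosaprepitant (weak), by name. Idelalisib, apalutamide, enzalutamide and mitotane are covered as antineoplastics.
- Not prohibited: strong and strongest inhibitors such as ketoconazole, itraconazole, posaconazole, voriconazole, clarithromycin and nefazodone. Also not prohibited: the strong inducers carbamazepine, phenytoin, rifampin and St. John's wort.

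**2. What existing safeguards cover**
- Exclusion 6 removes active infection needing systemic therapy at entry. Exclusions 17 and 18 (HBV/HCV, HIV) remove most need for the listed antivirals.
- From Cycle 2, doses are given "if the participant fulfills all the retreatment criteria within 3 days prior to the scheduled lurbinectedin infusion". Table 4 includes neutrophil and platelet limits and requires absence of active infection. An azole, clarithromycin or rifampin given for active infection therefore already coincides with a hold at the next dose.
- Prophylaxis with "colony-stimulating factors such as G-CSF or GM-CSF is mandated starting from Cycle 1 and during all subsequent cycles" protects neutrophils. Section 6.6 names nothing for platelets.
- Day 8 and Day 15 counts are routine in Cycles 1 and 2. Dose reductions (6.7) follow toxicity or delay.
- Remaining: prophylactic or mid-cycle anti-infectives, nefazodone, anticonvulsants and St. John's wort. None of these safeguards is triggered by use of a CYP3A4 drug.

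**3. Inhibitor benchmark (aprepitant only; linear kinetics, AUC = dose / clearance)**
- Exposure ratio = 1 / (1 − 0.42) = 1.72. If the approximate figure covers 40% to 45% (an assumption), the range is 1/0.60 = 1.67 to 1/0.55 = 1.82.
- Dose restoring usual exposure = 3.2 × 0.58 = 1.86 mg/m², below the lowest level in Table 6 (2.0 mg/m²). An interaction of this size could not be fully offset by the permitted reductions, so a hold is the better first response.

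**4. Inducer break-even against Table 6 (same assumption)**
- 3.2 / 2.6 − 1 = 0.23: a 23% rise in clearance puts the starting dose at the exposure of level −1.
- 3.2 / 2.0 − 1 = 0.60: a 60% rise puts it at level −2.
- These are thresholds, not predictions. The documents hold no lurbinectedin data with an inducer.

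**5. Monitoring gap (Table 3, 8.3.4)**
- Cycle 2 has three scheduled counts (Days 1, 8 and 15), 7 days apart. From Cycle 3 there is one per cycle, so 21 days apart, unless toxicity or a dose adjustment in the preceding cycle triggers Days 8 and 15.
- Projected 9-month Intervention Period: 9 × 30.4375 / 21 = 13.0 cycles, of which 13 − 2 = 11 have one scheduled count.
- Median PFS in the earlier lurbinectedin cohorts cited in Protocol 2.2.2 and 2.2.3 (1.4, 2.5 and 4.6 months) corresponds to 2.0, 3.6 and 6.7 cycles. On that guide, 0 to about 5 cycles lie beyond Cycle 2.

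**The case against.** Prohibiting what has been observed to interact, and asking sites to avoid the rest where possible, is a defensible approach. The sponsor reviews safety throughout, the Medical Monitor is available, and G-CSF/GM-CSF is now mandatory; nothing shows that the patients behind the aprepitant finding had it. Section 6.10.3 itself calls the interaction suggested. A participant on an inhibitor from baseline passes through two cycles of Day 8 and Day 15 counts, and Grade 4 haematological toxicity keeps those counts going. All of this stands, and it confines the gap to the residue in step 2. It does not close the gap: Medical Monitor contact depends on the site having a question, and no listed safeguard responds to the co-medication itself.

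Three stronger readings are tempting, and the documents do not support them.
- A reader might infer that there is no monitoring rule at all. Section 6.10.3 does ask for monitoring; what is missing is its content and any grading by potency.
- A reader might infer that the protocol has potency backwards. The aprepitant prohibition rests on observed lurbinectedin data and covers an antiemetic class, including fosaprepitant, which is ranked weak. It was never a potency rule.
- A reader might infer that foods are held to a firmer rule than drugs. The sentence in 5.3.1 is partly redacted, so the two cannot be compared.

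**Conclusion.** The point holds as a gap in the protocol's drug-interaction rules and is worth correcting at the next amendment. Strong and strongest CYP3A4 inhibitors and strong non-antineoplastic inducers are left to an unspecified instruction and investigator discretion. The exposed cases are mainly prophylactic or mid-cycle anti-infectives, nefazodone, anticonvulsants and St. John's wort, most clearly when started from Cycle 3. Under-exposure from an inducer is the least protected case.

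The only interaction size available is for a drug already prohibited: about 1.72-fold exposure under linear kinetics. A reader might infer a larger effect for strong inhibitors, but the documents give no lurbinectedin figure for any of them. Nor do they give a frequency of use, so the number of participants affected cannot be estimated.

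The conclusion covers readable text. Section 8.5 and part of 5.3.1 are redacted; 6.10.1 to 6.10.3, where such a rule belongs, show no redaction.

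**What to change.** - **Prohibit by class.** In 6.10.2, add strong and strongest CYP3A4 inhibitors and strong CYP3A inducers, with Appendix 7 as examples. Make the discretion sentence in 6.10.1 subject to 6.10.2.
- **Unavoidable strong inhibitor.** Require Medical Monitor agreement and hold lurbinectedin during co-administration. If dosing continues, require Day 8 and Day 15 haematology in every such cycle, including Cycle 3 and after. Counts act after exposure has risen and add nothing to the existing schedule in Cycles 1 and 2, so they are the fallback.
- **Unavoidable strong inducer.** Require a switch to a non-inducing alternative, or Medical Monitor agreement, before the next dose. Extra counts do not address under-exposure.

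Unapproved use would then count under the existing prohibited-medication subtype in SAP 8.3, with no SAP change.

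The cost is protocol wording, some medication switches and an occasional ineligible participant. For the few who continue on a strong inhibitor there are two extra counts per cycle from Cycle 3, at most 11 × 2 = 22 over the projected treatment period. These should be checked against the 415 mL blood limit in Protocol Section 8.

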7. DISCONTINUATION OF STUDY INTERVENTION AND PARTICIPANT DISCONTINUATION/WITHDRAWAL

Discontinuation from study *intervention* does not represent discontinuation from the *study* (Section 7.2). Participants may discontinue from study intervention at any time for any reason, or at the discretion of the investigator. In addition, a participant may be discontinued from study intervention by the investigator or sponsor for safety, behavioral, compliance, and/or administrative reasons. For participants that discontinue study intervention, all effort should be made to complete the procedures listed in the *EOT visit* (Table 3).

7.1. Discontinuation of Study Intervention

In rare instances, it may be necessary for a participant to permanently discontinue study intervention. If study intervention is permanently discontinued, the participant will return to the site 30 days (± 7 days) later for an EOT visit, and the participant will be followed for OS. For participants who discontinue treatment due to reasons other than disease progression, death, withdrawal of consent from study, or lost to follow-up, radiographic assessment should continue until disease progression, initiation of new anticancer therapy, death, withdrawal of consent from study, EOT Visit, lost to follow-up, or study termination. A radiological tumor assessment will be performed at the EOT visit for these participants if not performed within 7 days of the last treatment assessment visit. See the SoA (Table 3) for data to be collected at the time of discontinuation of study intervention and follow-up and for any further evaluations that need to be completed.

A participant must be discontinued from study intervention for any of the following reasons:

- The participant requests to discontinue study intervention
- The participant has an AE that may compromise the participant's continued participation (see Section 8.4.3 for follow-up guidelines)
- The participant experiences a Grade ≥ 3 hypersensitivity reaction
- The participant experiences Grade ≥ 3 rhabdomyolysis
- The participant has any of the clinical conditions as noted in Section 6.7, which cannot be resolved with either of the following attempts:
 - The participant requires > 2 dose reductions
 - The participant requires a treatment delay > 3 weeks from the due date because of treatment-related toxicity (except if objective clinical benefit is observed, with the Sponsor's agreement)
- The participant has a positive serum pregnancy test or becomes pregnant during the study (Appendix 5 and Section 8.4.5)
- The participant is noncompliant with study intervention or procedures
- The sponsor decides to terminate the study or an individual cohort for any reason
- The investigator determines the participant should not continue on study intervention

- The participant has confirmed radiological disease progression as per RECIST v1.1

7.2. Participant Discontinuation/Withdrawal From the Study

- A participant may withdraw from the study at any time at his/her own request or may be withdrawn at any time at the discretion of the investigator for safety, behavioral, or compliance reasons.
- At the time of discontinuing from the study, if possible, an E/D visit should be conducted within 30 days, as shown in the SoA. See SoA for data to be collected at the time of study discontinuation and follow-up and for any further evaluations that need to be completed.
 - The participant will be permanently discontinued from both the study intervention and from the study at that time.
- If the participant withdraws consent for disclosure of future information, the sponsor may retain and continue to use any data collected before such a withdrawal of consent.
- If a participant withdraws from the study, he/she may request destruction of any samples taken and not tested, and the investigator must document this in the site study records.

